7.1. Individual data will not be shared among participants. Aggregate findings will be disseminated to the community in partnership with WellShare International (community partner).

8. Study Duration

- 8.1. Describe:
 - 8.1.1. The duration anticipated for adolescents participating in Phase 1 focus group is 1 hour. The duration anticipated for an individual participant's participation in the Phase 2 activities of the study is approximately 20 hours over 8 weeks including intervention and administrative visits.
 - 8.1.2. The duration anticipated to enroll Phase 1 study participants is 1 week.

 Duration anticipated to enroll all Phase 2 study participants is 3 months
 - 8.1.3. The duration anticipated to complete all study procedures and data analysis is 12 months

9. Study Population

9.1 Inclusion Criteria:

Adult inclusion criteria:

a) Above the age of 18

PROTOCOL TITLE: MBI Intervention with war-affected families

VERSION DATE: 3/2/2022 v6

b) Karen refugees resettled to the United States greater than one year prior to enrollment

- c) Caregiving responsibility for at least one child between the ages of 11 and 18
- d) Reported primary or secondary torture or war trauma exposure, based on assessments conducted during UMN IRB STUDY00000729
- e) Participation in UMN IRB STUDY00000729 and having agreed to be contacted for future research

Youth inclusion criteria:

- a) Ages 11 to 18
- b) Living in the home with the primary caregivers
- c) Considered a dependent of the primary caregivers (still in high school or transitioning from school to work force, not married and/or raising their own children will take individual youth circumstances into consideration individually to make a determination of dependence)

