3.1 Primary Endpoint/Event/Outcome: Results will demonstrate the feasibility of community based participatory research strategies, recruitment, retention, fidelity, data collection procedures, and the acceptability and adaptability of the intervention. We are establishing training procedures where the PI and the community health interventionists will be trained and evaluated in the delivery of the intervention. Additionally we are merging two evidence based interventions, both of which will be adapted contextually to the context of a homebased intervention for war-affected families with adolescent youth.

Hypothesis 1a: The CBPR design utilizing CHWI will demonstrate high intervention impact measured by intervention fidelity, rates of completion of study milestones, and high participant and CHWI satisfaction.

Hypothesis 1b: Recruitment and retention will be robust. The study team will meet recruitment targets and 85% of families will complete FMBI sessions and structured assessments within 3 months of enrollment.

Page 11 of 45

PROTOCOL TITLE: MBI Intervention with war-affected families

VERSION DATE: 3/2/2022 v6

Hypothesis 1c: Acceptability and sustainability will be demonstrated through qualitative reports of engagement, safety of the intervention, readiness to adopt, uptake, and perceived cultural congruence.

3.2.Secondary Endpoint(s)/Event(s)/Outcome(s): Though purposely not powered to infer a causal relationship, we will examine trends in outcomes related to physical complaints and mindfulness related processes in youth and parents. These outcomes include: youth adjustment; mindfulness; emotion regulation; family functioning and physiological regulation.

Hypothesis: FMBI will demonstrate preliminary improvements in outcomes listed above.

4. Study Intervention(s)/Interaction(s)

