1. Description: The Family Mindfulness Based intervention will consist of two evidence based interventions, adapted contextually to the circumstances of war-affected families in resettlement, and integrated. The first intervention is the After Deployment Adaptive Parenting Tools (ADAPT) intervention. This is a 14 session group-based mindful parenting intervention originally developed to increase emotion regulation among military caregivers with young children and improve youth adjustment.³³⁻³⁶ Parents will be invited to participate in individual interviews post-program. The second intervention is Learning To BREATHE, a 6 session group-based intervention targeting adolescent mindfulness.³⁷⁻⁴¹ The adapted and merged intervention will be delivered to individual families (home-based) in twice weekly sessions over a 7-week period by two community health worker interventionists. Learning to Breathe was determined during pilot testing to be more effective in the group format and the study team will return to the original delivery format of 6 group sessions. In addition to intervention sessions, there will be an enrollment visit, where consent and pre-intervention assessments are completed. Post-assessments and focus groups will be conducted immediately post-intervention. The administrative and 7-week intervention period will cover topics as described in the following table.

| Table 1. Schedule of visits including elements of the family mindfulness based | | | |
|--|--|---|--|
| Week | Caregiver (reflects adapted ADAPT intervention) | Youth (reflects adapted Learning to BREATHE intervention) | |
| Pre- | Enrollment and Consent | Enrollment and Assent | |
| Intervention (120 minutes) | Demographics | Demographics | |
| (120 minutes) | Pre-assessments (listed table 2: caregiver, family, all) | Pre-assessments (listed table 2: youth, family, all) | |

Page 12 of 45

PROTOCOL TITLE: MBI Intervention with war-affected families

VERSION DATE: 3/2/2022 v6

| 1 (60 minutes) | Building Blocks of Resistance | Body |
|--|--|-----------------------------------|
| | Give Effective Directions | Check in and practice |
| 2 (60 minutes) | Teach New Behavior | Reflection |
| | Recognizing emotions | Check in and practice |
| 3 (60 minutes) | Responding to Emotions | Emotions |
| | Setting Limits | Check in and practice |
| 4 (60 minutes) | Following Through | Attention |
| | Communicate with Children | Check in and practice |
| 5 (60 minutes) | Solving Problems | Tenderness |

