| | Managing Conflict | Check in and practice |
| 6 (60 minutes) | Monitor children's activities | Health Mind Habits |
| | Responding to Children's Emotions | Check in and practice |
| 7 (60 minutes) | Building Skills: Linking home and school | |
| Post- Intervention (120 minutes) | Post intervention assessments | Post intervention assessments |
| Optional focus g | groups by role (60-90 minutes): Separ | ate maternal, paternal, and youth |

tocus groups

5. Procedures Involved

5.1. Study Design:

We will test the feasibility of the family mindfulness-based intervention with a resettled population of war-affected families through a nonrandomized partial cluster feasibility trial with embedded qualitative procedures.

This will occur in 2 phases:

PROTOCOL TITLE: MBI Intervention with war-affected families

VERSION DATE: 3/2/2022 v6

Phase 1: Intervention adaptation and Community Health Worker Interventionist (CHWI) training through the delivery of the intervention to Community Leadership Board (CLB) members and adolescent focus group

Phase 2: Preliminary feasibility testing of the FMBI with members of the Karen community

5.2. Study Procedures:

Phase 1:

Community Leadership Board

The CLB will be made up of 4-7 Karen professionals representing prominent local organizations supporting Karen refugees in resettlement. Representatives will have lived cultural and historical expertise as well as professional expertise supporting the resettled community from mental health and social services perspectives. The expertise of the board ensures culturally centered preparations for intervention dissemination. The CLB will take an active role in the adaptation of the intervention. At the end of Phase 1 the board will determine the frequency of meetings through Phase 2.

CHWI Training

- Watch 25 hour ADAPT training video
- 50 hours of training with certified ADAPT facilitator for training, role play, and feedback
- ADAPT facilitator will provide 80 hours coaching based on based on recorded sessions
- 15 hours training with certified Learning to Breathe facilitator

Adaptation/CHWI coaching

- In Phase 1 the CLB will meet twice per week for 6 weeks. At each meeting the CHWI will present an intervention module to the CLB via Zoom. This will be recorded and later watched by the intervention facilitator to provide coaching to the CHWI. Members of the CLB will be aware of and agree to the session recording.

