An optional later 60-90 minute focus group will be offered 1-month post-intervention for youth. Parents will be invited to participate in individual interviews. Cost of transportation and childcare will be supported for focus group participants and each participant will receive a \$15 gift card for participation. Questions will target success and challenges participants have had implementing the skills taught in the intervention, as well as general perceptions of the intervention 1-month after the program end. Coordinators will have participated in the *refinement and implementation* of the intervention in Aim 1. Study coordinators and local interventionists will be trained intervention facilitators based at the University of Minnesota. Fidelity observations will be made weekly by study team members/trainers. As part of feasibility testing we will monitor participant adherence to the study protocol and the challenges that prevent families' full participation in attending interventions sessions. Study visits that take place +/- 2 days of target visit date will be considered 'on time'. Visit outside of this timeframe will be considered delayed. If a family member misses a scheduled visit, it will be documented as "missed".

Activities of phase 2 are contingent on the completion of phase 1 and IRB approval of all modifications to the intervention and/or proposed study protocol.

Regarding in person versus remote interactions, we are developing two models, depending on the circumstances of Covid-19 in the Summer-Fall 2021 (intensive data collection phase). We plan to follow all Federal/CDC guidelines as appropriate. We anticipate a hybrid implementation in that we will have families that prefer the telehealth option and familes that prefer in person.

Page 16 of 45

PROTOCOL TITLE: MBI Intervention with war-affected families

VERSION DATE: 3/2/2022 v6

 Model A - WellShare CHWs are currently conducting telehealth visits by phone or video. If the circumstances surrounding Covid-19 persist into the summer-fall 2021 we will conduct all study procedures through remote technology.

• Model B – If the circumstances allow, we will plan for data collection and intervention sessions to be conducted in person, outdoors.

We are planning for study personnel and participant PPE should this be necessary. The School of Nursing Office for Nursing Research and Scholarship will provide PPE funds if necessary.

5.2.1.

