| Emotion Regulation Skills Questionnaire (ERSQ) | Emotion regulation | A 27-item assessment of emotion regulation skills described in the ART ⁸³ model | My physical sensations were a good indication of how I was feeling. | α = .96 | Grant et al. 2018 ³⁰ |
| Family Functionin | g (all complete | e) | | | |

PROTOCOL TITLE: MBI Intervention with war-affected families

VERSION DATE: 3/2/2022 v6

| Family Adaptability and Cohesion Scale IV (FACES) | Family functioning | A 42-item assessment of cohesion & flexibility | Family members are supportive of each other during difficult times. | Alpha reliability range subscales: α = .7789 | Olson, 2011 ²⁷ |
|---|------------------------------|---|---|--|--|
| Physiological Regu | ulation (all con | nplete) | | | |
| Cohen- Hoberman Inventory of Physical Symptoms (CHIPS) | Physical health status | A 39-item assessment of perceived burden from physical symptoms | How much were you bothered by: Back pain Constipation Dizziness | α = .88 | Cohen & Hoberman, 1983 ³¹ |

- 5.3. Follow-Up: Currently we plan to collect pre/post intervention and focus group data only. If additional funds are obtained will add a 6 month follow up assessment. If this is the case, we will submit an addendum to this protocol. Parents who complete the ADAPT intervention will be invited to conduct a 1:1 in depth interview about their experiences in the program. This will occur in the home and an incentive of \$10 will be provided.
- 5.4. Individually Identifiable Health Information: This study will include individually identifiable health information but will not include data from medical records. See section 18.0. Participants will be asked to sign a combined ICF/HIPAA form before completing any study procedures.

6. Data Banking

- 6.1. Storage and Access: De-identified data collected from the pre- and post- assessment measures in this study may be used in collated fashion for future peer-reviewed publications or other scientific communications.

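### Section 5.3 addresses the parent interview to parents who complete ADAPT, while Sections 4 and 5.2 set no such condition; applied literally, 5.3 draws the interview evidence on acceptability from completers

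*Combined protocol and SAP*

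**What the plan says.** Parent interviews are described in three main places, and parent focus groups in a fourth.

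- **Section 5.3 (Follow-Up):** "Parents who complete the ADAPT intervention will be invited to conduct a 1:1 in depth interview about their experiences in the program". The interview is held at home with a $10 incentive. The same section opens by stating "Currently we plan to collect pre/post intervention and focus group data only", which does not list interviews.
- **Section 4 (Description):** "Parents will be invited to participate in individual interviews post-program". The same paragraph says "Post-assessments and focus groups will be conducted immediately post-intervention".
- **Section 5.2 (Phase 2):** "Parents will be invited to participate in individual interviews". The focus group one month after the intervention is offered here to youth.
- **Table 1, last row:** optional focus "groups by role (60-90 minutes"), with separate maternal, paternal and youth groups.

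The use of this evidence is set in Section 3.1, Hypothesis 1c: "Acceptability and sustainability will be demonstrated through qualitative reports of engagement, safety of the intervention, readiness to adopt, uptake, and perceived cultural congruence". Section 17.1 analyses interview and focus group transcripts by content analysis. Sections 9.3 and 12.1 also mention final evaluation interviews, with no completion condition.

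**The concern.** Acceptability is part of the primary endpoint and is to be judged from qualitative reports. Table 2 lists the pre/post instruments and contains no acceptability or satisfaction scale, so transcripts carry much of the weight. Whether a parent completes the sessions is closely tied to whether the parent found the programme acceptable and culturally fitting. An interview sample chosen on completion is therefore chosen on something near the quantity being assessed, and the parents best placed to describe poor fit may not be heard.

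There is also a practical problem. Staff working from Section 5.3 and staff working from Section 5.2 could invite different parents. Because completion is not expressed as a number of the 14 ADAPT sessions, two people applying Section 5.3 could also disagree with each other.

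**Working it through.** The plan gives no figure to reproduce here, so the check is mainly a comparison of text.

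**Who is invited to the interview**

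| Place | Invitee | Completion condition |
|---|---|---|
| Section 4 | parents, after the programme | none; a time point only |
| Section 5.2, Phase 2 | parents | none |
| Section 5.3 | parents who complete ADAPT | yes, undefined |
| Sections 9.3 and 12.1 | assigned participants, helped through to final interviews | none |

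Section 5.3 alone sets a condition.

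**In which format**

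Sections 4, 5.2 and 5.3 all give parents interviews. Table 1 keeps optional maternal and paternal focus groups, also without a completion condition. Nothing says whether these groups run beside the interviews or were replaced by them.

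**What else would be known about parents who attend little or stop**

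- Section 5.2: "we will monitor participant adherence to the study protocol and the challenges that prevent" full participation, and missed visits are documented.
- Section 13.2: for a parent who withdraws, reasons are discussed and the date and reason are recorded; other data collection ends. A parent who misses sessions but stays enrolled is not covered.
- Section 20.2: distress reports are taken at visits and by telephone.

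These cover barriers, reasons and distress. None is an in-depth interview, and Section 17.1 names only interview and focus group transcripts for content analysis.

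**Scale, as illustration only**

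Inputs: N = 10 to 12 families (Section 9.3) and the 85% family target in Hypothesis 1b, taken as if it were the true rate. The 95% and 70% rates are assumptions. Families are assumed to complete independently.

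Expected families not completing = N × (1 − p). Chance of at least one = 1 − p^N.

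| p | Expected families not completing | Chance of at least one |
|---|---|---|
| 0.95 | 10 × 0.05 = 0.5; 12 × 0.05 = 0.6 | 1 − 0.95^10 = 0.401; 1 − 0.95^12 = 0.460 |
| 0.85 | 10 × 0.15 = 1.5; 12 × 0.15 = 1.8 | 1 − 0.85^10 = 0.803; 1 − 0.85^12 = 0.858 |
| 0.70 | 10 × 0.30 = 3.0; 12 × 0.30 = 3.6 | 1 − 0.70^10 = 0.972; 1 − 0.70^12 = 0.986 |

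The 85% target refers to families completing sessions and structured assessments within three months. A family can miss it through youth sessions or a late assessment while both parents finish ADAPT, and one parent can stop while the other continues. The table therefore shows only that some non-completion is likely in a sample of this size. It does not count the parents whom Section 5.3 would leave out.

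**The case against.** The strongest reply is that the exclusion is inferred. Section 5.3 says whom the team will invite and does not say that others will not be invited. Completing ADAPT may be no more than a loose way of saying after the programme, in line with Sections 4 and 5.2. The sentence restricting collection to pre/post and focus group data stands next to a possible six-month assessment, so it may be meant to rule out longer follow-up rather than interviews. Early stoppers are not invisible: barriers, withdrawal reasons and distress are recorded, Section 14.1 treats negative reactions that need a clinician as information for refining the intervention, and Hypothesis 1b reports retention separately. Hypothesis 1c speaks of qualitative reports and does not single out interviews.

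Most of this stands, and it limits the point. It does not remove it: on the lenient reading the sections still need to agree, and the literal reading is open to any staff member who follows Section 5.3.

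A reader might go further in three ways that the documents do not support.

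- **That the protocol excludes non-completers and so biases acceptability upward.** The wording is not exclusive, no acceptability proportion is planned, and neither the direction nor the size of any bias can be derived.
- **That Section 13.2 should be changed so that withdrawn parents can be interviewed.** Reconciling Section 5.3 does not require it. It would loosen a clear stop on data collection in a population that, under Section 10, may include people who fear negative consequences.
- **That themes should be reported by completion status.** With very few non-completers in a small community, and interventionists taking part in the analysis (Section 17.4), this could make individuals identifiable.

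**Conclusion.** The point holds in a limited form. Sections 4, 5.2 and 5.3 do not agree on which parents are invited to the interview, and the condition in Section 5.3 is undefined. If Section 5.3 is followed literally, interview evidence bearing on a component of the primary endpoint comes from completers, and other sources make up only part of the loss. This rests on the literal reading being the one applied, and on the status of the parent focus groups staying unsettled. No size of bias can be stated. The paired pre/post analysis is not touched. The matter is worth correcting because the remedy is small and the views of parents who stop attending may be hard to collect later.

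**What to change.** 1. In Section 5.3, address the interview to all enrolled parents who have not withdrawn, whatever their attendance, so that it agrees with Sections 4 and 5.2. The invitation then no longer depends on a definition of completion.
2. Reconcile this with the maternal and paternal focus groups in Table 1 and with the sentence in Section 5.3 on what data are collected: state whether parents give interviews, focus groups or both.
3. Report how many parents were invited, interviewed and declined, by attendance at the 14 sessions.

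Section 13.2 can stay as it is.

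Cost: each additional home interview carries the $10 incentive already in Section 5.3; four more, for example, would be 4 × $10 = $40. Interviewer time, travel, and transcription or translation come on top and cannot be priced, because the plan gives no interview length. An IRB wording change is needed. Some parents who stopped attending will decline, and withdrawn parents remain outside, so the gap is reduced and made visible rather than closed.

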9.2 Exclusion Criteria

Exclusion criteria (applies to both adult and youth participants):

- a) Self-reported or study team observed severe or unstable mental or physical illness such as: acute psychosis, presence or risk of safety concerns, and/or a physical disability or illness, which prevents the potential participant from engaging in the study activities. Youth will be excluded if screening is positive for PTSD. Caregivers will not be excluded if mental health screening is positive for PTSD/severe depression.
- b) Nonbiological caregiving relationships with child
- c) If one member of the family declines to participate in the initial enrollment, the family will be excluded. If the randomly selected index youth declines to participate, we will open enrollment to other youth in the family that meet the inclusion criteria.
- 9.3 Screening: Karen families will be recruited from an existing cohort of 96 Karen families that participated in preliminary observational studies and gave consent to be contacted for potential involvement in future phases of the research (UMN IRB STUDY00005512 and STUDY00000729). Participation in previous study phases will not impact the proposed trial. Two Karen community health worker interventionists will be prepared to assist potential and assigned participants in all aspects of the study—from recruitment and consent processes, to intervention delivery, data collection, and final evaluation interviews.

In phase 1 our recruitment target is up to 12 adolescent youth age 11-18 to participate in 5-6 member focus groups, each group meeting up to 3 times. One parent will give verbal consent over the phone. Youth assent will be confirmed at the beginning of the focus group session. Focus group sessions will take place over Zoom and will be facilitated by the CHWI with the PI present. Zoom sessions will be audio only recorded and any Karen language discussion will be transcribed by CHWI. All transcriptions will be de-identified.

Page 21 of 45

PROTOCOL TITLE: MBI Intervention with war-affected families

VERSION DATE: 3/2/2022 v6

In phase 2 our recruitment target is N=10-12 families, inclusive of the maternal caregiver, paternal caregiver (when present), and one randomly selected index youth per family age 11-18. At the initial contact with potential participants (phone call), the community health worker/Karen interventionist will explain study procedures such as voluntary participation and what participation in the intervention entails. Potential participants will be offered the opportunity to ask questions about study procedures. A second, in person encounter will be scheduled if the potential participant expresses interest in study participation. At a second encounter (face to face in participant homes or preferred alternative location or via Zoom if remote is preferred) continued interest in participation will be assessed. Parents and youth will be screened for eligibility, and informed consent and assent will be obtained. Baseline data collection will be obtained at this second encounter. Intervention sessions will begin within one month of enrollment.

10. Vulnerable Populations

10.1. Vulnerable Populations:

| Population / Group | Identify whether any of the following populations will be targeted, included (not necessarily targeted) or excluded from participation in the study. |
|--|--|
| Children | Targeted Population |
| Pregnant women/fetuses/neonates | Included/Allowed to Participate |
| Prisoners | Excluded from Participation |
| Adults lacking capacity to consent and/or adults with diminished capacity to consent, including, but not limited to, those with acute medical conditions, psychiatric disorders, neurologic disorders, developmental disorders, and behavioral disorders | Excluded from Participation |
| Non-English speakers | Included/Allowed to Participate |
| Those unable to read (illiterate) | Included/Allowed to Participate |
| Employees of the researcher | Excluded from Participation |
| Students of the researcher | Excluded from Participation |

Page 22 of 45

PROTOCOL TITLE: MBI Intervention with war-affected families

VERSION DATE: 3/2/2022 v6

| Undervalued or disenfranchised social group | Targeted Population |
|---|---------------------------------|
| Active members of the military (service members), DoD personnel (including civilian employees) | Included/Allowed to Participate |
| Individual or group that is approached for participation in research during a stressful situation such as emergency room setting, childbirth (labor), etc. | Excluded from Participation |
| Individual or group that is disadvantaged in the distribution of social goods and services such as income, housing, or healthcare. | Targeted Population |
| Individual or group with a serious health condition for which there are no satisfactory standard treatments. | Included/Allowed to Participate |
| Individual or group with a fear of negative consequences for not participating in the research (e.g. institutionalization, deportation, disclosure of stigmatizing behavior). | Included/Allowed to Participate |
| Any other circumstance/dynamic that could increase vulnerability to coercion or exploitation that might influence consent to research or decision to continue in research. | Included/Allowed to Participate |

10.2 Additional Safeguards:

The study team will base a trauma informed approach on SAMHSA's 6 KEY PRINCIPLES OF A TRAUMA-INFORMED APPROACH:

- 1. Safety
- 2. Trustworthiness and Transparency
- 3. Peer Support
- 4. Collaboration and Mutuality
- 5. Empowerment, Voice and Choice

PROTOCOL TITLE: MBI Intervention with war-affected families

VERSION DATE: 3/2/2022 v6

6. Cultural, Historical, and Gender Issues

The framework will be implemented through a number of strategies, including but not limited to: Karen community health worker interventionist model, stakeholder-led intervention development/adaptation, home-based intervention delivery, participant led consent and assent discussions, family involvement, and community advisory board input/oversight.

Illiterate:

Patients who are illiterate may not be known, research staff will not be asking a direct question about literacy to potential participants. However, if it's made known to us that the patient is illiterate we will take extra care to go through the consent form and read it to the potential participant. Vulnerability for this group will not be increased by participating in this study. Undervalued and Disadvantaged:

Disadvantaged and disadvantaged people may not be known, research staff will not be asking a direct question about socioeconomic status to potential participants. Vulnerability for this group will not be increased by participating in this study.

Fear of Negative consequences:

Individuals with a fear of negative consequences for not participating in the research (e.g. institutionalization, deportation, disclosure of stigmatizing behavior) are not targeted but may be enrolled. All participants will be fully informed that the study is completely voluntary and that they may withdraw participation at any time. They will also be reminded that their relationship with their provider or the UMN will not be affected by their decision whether or not to participate in this study.

